1 OBJECTIVES

1.1 Primary Objective

The primary objectives of this prospective pilot study is to (1) determine the feasibility and reproducibility of 3D contrast enhanced ultrasound imaging in liver cancer patients undergoing Stereotactic Ablative Radiotherapy and (2) evaluate whether there are treatment induced early changes in imaging metrics derived from 3D contrast enhanced ultrasound. This study will provide valuable insight as to the potential of baseline and/or early post-treatment 3D ultrasound perfusion characteristics (measurements of blood-flow) of primary and metastatic liver tumors to predict tumor response to Stereotactic Ablative Radiotherapy. Our underlying goal is to assess whether early perfusion changes at 0-7 days after SABR initiation can be used as a non-invasive early biomarker for treatment response assessment.

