During the unenhanced ultrasound examination, the morphology and localization of the target FLL will be evaluated using gray scale ultrasound and color/power Doppler modes. The target lesion will be identified using gray scale ultrasound and its location will be identified using Coineaud's system. Then, either color Doppler imaging or power Doppler imaging should be used to study the morphology/vascularity of the target lesion and surrounding parenchyma. Specific measurements with Spectral Doppler may be used depending on the presence and/or visualization of vessels.

Contrast-Enhanced Ultrasound Examination

The following protocol will be used, according to published literature (23):

An infusion of 1.3 mL of Definity diluted in 50 mL of saline will be administered using an injection pump. Two minutes will be allowed for the infusion to reach a steady level before disruption-replenishment. Measurements will be performed two times (to assess reproducibility of the replenishment curves analysis following microbubble destruction and replenishment of microbubbles into the US field-of-view).

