10.1.3 Measurement Methods

Contrast Agent Administration

The US contrast agent will be perflutren lipid microspheres (Definity; Lantheus Medical Imaging, North Billerica, Mass). Patients will receive an infusion of 1.3 mL of perflutren lipid microspheres diluted in 50 mL of saline delivered up to 10 mL/min by using an injection pump (Medfusion 3500; Smiths Medical, Dublin Ohio). Two minutes will be allowed for the infusion to reach a steady level before disruption-replenishment measurements were performed.

Imaging System Parameters

Contrast-specific imaging will be performed with an abdominal matrix-array transducer (PMPI mode, Philips iU22 with X6-1; Philips Ultrasound, Bothell Wash). Low-mechanical-index (MI) nonlinear imaging (MI, 0.06) will allow visualization of the microbubbles nondestructively. Persistence and other post-processing will be disabled to minimize temporal and spatial averaging. Time-gain controls will be aligned to the center line. Receive gain, dynamic range, image depth, and transmit focus will be optimized for each patient at the baseline examination, and then identical settings will be used at follow-up. Disruption-replenishment data will be collected for approximately 30 seconds following each 1-second, 8-frame flash at an MI of 1.3. Frame rates ranged from 7 to 12 Hz. Data will be stored in a compressed “native” format to allow linearization.

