10.1.4 Measurement Time Points

The probe will be held steady throughout each acquisition. During the infusion, continuous 3D data will be collected and two disruption-replenishment acquisitions will be performed.

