12 STATISTICAL CONSIDERATIONS

12.1 Statistical Design

The primary objectives of this pilot study is to (1) determine the feasibility and

reproducibility of 3D contrast enhanced ultrasound imaging in liver patients undergoing Stereotactic Ablative Radiotherapy and (2) evaluate whether there are treatment induced early changes in imaging metrics derived from 3D contrast enhanced ultrasound. Specifically, we will perform exploratory analysis for testing the following hypotheses:

12.2 Outcome Measurements:

Primary endpoints:

- To characterize the reproducibility of 3D DCE-US by estimating the concordance correlation coefficient (30,31) for repeated 3D DCE-US measures (see Section 10.1.6, Image analysis and derived measures).
- To determine the variance in the relative changes of repeated 3D DCE-US measures.
- To provide summary statistics of the relative changes in 3D DCE-US measures before and after SABR.

Secondary endpoint:

- To provide relative number of 3D DCE-US examinations in which fusion to CT is possible with tracking of the ultrasound transducer.

12.3 Analysis plan:

This is an exploratory pilot study designed with a primary objective to evaluate (1) the feasibility and reproducibility of 3D DCE-US in cancer patients undergoing SABR for liver lesions and (2) the magnitude of the differences in perfusion measures before and after SABR. Future studies will seek to understand if 3D DCE-US perfusion baseline values or changes have predictive power for clinical endpoints in SABR treatments. The knowledge gained from this study will aid in calculating the appropriate sample size for such studies. The main focus here is on understanding the discrepancies in measures from repeated acquisitions and differences in measures before and after SABR. Thus the data will be analyzed as follows:

- Estimation the concordance correlation coefficient (30, 31) for repeated 3D DCE-US measures (see Section 10.1.6, Image analysis and derived measures) as a measure of reproducibility. Concordance correlation values between 0.9 and 0.95 will be interpreted as moderate reproducibility and values between 0.95 and 0.99 will be interpreted as substantial reproducibility based on the following scale for the concordance correlation coefficient: Poor, < 0.9; moderate, 0.9 – 0.95; substantial 0.95 – 0.99, nearly perfect >0.99.

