- Histogram analysis and summary statistics (mean, median, variance, and maximum) of the relative changes (difference/average) of repeated 3D DCE-US measures. (Small variance and zero mean of the relative changes will be indicative of highly reproducible 3D DCE-US measures).
- Histogram analysis and summary statistics (mean, median, variance, and maximum) of the relative changes (difference/baseline) in 3D DCE-US measures before and after SABR. Large mean differences will be indicative of treatment (SABR) effect.

- Calculation of proportion of 3D DCE-US examinations in which fusion to CT is possible with tracking of the ultrasound transducer. Calculation of proportion of 3D DCE-US examination in which repeated scans is successful. These proportions are metrics of feasibility (target 80%-90%). Successful fusion to CT in particular is important metric is 3D DCE-US is to be explored as add-on imaging for treatment planning in further studies.

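### Section 12.3 reads a SABR effect from a large mean relative change, without a confidence interval or a comparison with repeat-scan noise

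*Combined protocol and SAP*

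**What the plan says.** Section 12.1 gives the second primary objective as to "evaluate whether there are treatment induced early changes in imaging metrics derived from 3D contrast enhanced ultrasound". Section 12.2 turns this into an endpoint: "To provide summary statistics of the relative changes in 3D DCE-US measures before and after SABR". Section 12.3 then lists the outputs (histogram, mean, median, variance and maximum) and the reading rule, for the "relative changes (difference/baseline) in 3D DCE-US measures before and after SABR. Large mean differences will be indicative of treatment (SABR) effect".

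The bullet just before it in section 12.3 summarises repeat acquisitions in the same way, but divides the difference by the average of the two values. The repeats are made within one session. Section 4 says "Measurements will be performed two times (to assess reproducibility of the replenishment curves analysis following microbubble destruction", and section 10.1.4 says "During the infusion, continuous 3D data will be collected and two disruption-replenishment acquisitions will be performed". Neither section 10 nor section 12 says whether the two acquisitions at a visit are averaged before the change from baseline is formed.

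There are two scans after the start of SABR (section 3.5): one at 0-7 days after the first fraction and one at 2-4 months. Sections 12.2 and 12.3 do not say which is meant. Section 1.1 points to the first, since its underlying goal is to learn whether "early perfusion changes at 0-7 days after SABR initiation can be used as a non-invasive early biomarker".

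**The concern.** The sentence on large means is the only statement of how objective 2 will be read. A mean of 20 noisy ratios will differ from zero even if SABR changes nothing, and the plan has no yardstick for how far. Elsewhere section 12.3 does supply one: cut-offs for the concordance coefficient, and an 80%-90% target for the feasibility proportions.

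The repeat acquisitions are the natural noise reference. However, the plan never links them to the SABR change, and the two results use different denominators. Followed as written, the rule could present noise as a treatment effect. Section 12.3 also says that the results will help to size later studies, so the uncertainty of the change is itself a product of this pilot.

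**Working it through.** There is no figure in the plan to reproduce: sections 12.4 and 12.5 give 20 patients and state that information for a calculation is lacking.

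**Inputs.** From the documents: n = 20, two acquisitions per visit, change = difference/baseline. Assumed: CV of one acquisition 10% to 50%, lognormal noise, equal CV at both visits, errors independent between visits and acquisitions, and the same true change d in every patient.

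**Noise alone (d = 0), acquisitions averaged.** 100,000 simulated trials of 20 patients per CV:

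| CV | SD of one patient's change | Central 95% range of the trial mean |
|---|---|---|
| 10% | 10.1% | -3.9% to +4.9% |
| 20% | 20.5% | -6.7% to +11.3% |
| 30% | 31.7% | -8.6% to +19.0% |
| 50% | 57.6% | -10.6% to +39.9% |

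If a single acquisition is used, which the plan leaves open, the ranges widen to about -8% to +18% at CV 20% and -10% to +31% at CV 30%. As an illustration only, since no document calls 10% large: with averaging, the mean passes 10% in either direction in 4.8% of null trials at CV 20% and 22.6% at CV 30%.

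**Interval.** The 95% half-width for the mean is t(19, 0.975)/sqrt(20) = 0.468 times the SD. At CV 30% this is 0.468 x 31.7 = 14.8 points. For the median, the 6th to 15th ordered values of 20 cover 1 - 2P(Bin(20, 0.5) <= 5) = 95.9%.

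**Noise benchmark.** To first order, difference/average of two single acquisitions has SD sqrt(2) x CV, or 28% at CV 20%. The change between two visit averages has noise SD of about CV, or 20%. The repeat SD must therefore be divided by sqrt(2) before it is set beside the SD of the changes, and by a further sqrt(20) before it is set beside the mean. It may also be too small, because repeats share one infusion. If half of the log variance is shared within a session, repeats show a CV of 21.0% when the total is 30%.

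**Noise in the denominator.** Write baseline = mu(1 + e1) and follow-up = mu(1 + d)(1 + e2), with independent errors. Then E[difference/baseline] = (1 + d)E[1/(1 + e1)] - 1, which is about d + (1 + d)CV^2, where CV is that of the baseline value used. At d = 0:
- single acquisition: +1.0, +4.0, +9.0 and +25.0 points at CV 10, 20, 30 and 50%;
- two averaged acquisitions: +0.5, +2.0, +4.5 and +12.4 points.

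With averaging, this is 0.22, 0.44 and 0.64 of a standard error at CV 10, 20 and 30%, and about one at CV 50%. With a single acquisition, a correlation of 0.5 between the log errors of the two visits also roughly halves it (+2.0 points at CV 20%, +4.4 at 30%).

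For a true 20% fall with averaging, results at CV 10, 20, 30 and 50% are:
- average of the mean: -19.6, -18.4, -16.4 and -10.1%;
- average of the median: -20.0, -19.9, -19.7 and -19.2%;
- coverage of -20% by the mean's interval: 94.8, 94.2, 93.3 and 90.6%;
- coverage by the median's interval: about 96% throughout.

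At CV 30% the average interval width is 23.2 points for the mean and 28.2 for the median.

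**The case against.** The best defence is that this is an exploratory pilot with descriptive aims. The mean, variance and histogram are planned, so a reader who knows n can form mean +/- 0.468 SD. Repeat noise is a primary endpoint. The sentence on large means is loose interpretation, not a decision rule. Most of this stands. The interval is omitted but recoverable, and noise is measured. What remains is that the plan itself infers a treatment effect from the mean and does not make either comparison.

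Three stronger readings are tempting, and the documents do not support them:

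- **That bias makes the planned mean invalid.** Its size rests on a CV that the documents do not give and on independence between visits. At CV 10% to 30% with averaging, the mean's interval still covers 93% to 95%. The median is already planned.
- **That log ratios should replace the planned scale.** The log ratio targets a geometric mean, whereas section 12.3 asks for the magnitude of the differences. Eligibility covers both primary tumours and metastases, so responses may vary. With true changes varying around an arithmetic mean of -20% (log-SD 0.5), the log-ratio interval covers that mean in only 82% to 85% of trials at CV 10% to 30%, against 93% to 95% for the ordinary mean. If half of lesions are unchanged and half fall 80%, the geometric mean is sqrt(0.2) - 1 = -55% against an arithmetic -40%. Zero values cannot be used.
- **That the within-patient ratio is a poor basis.** Section 10.1.3 says that scanner settings are "optimized for each patient at the baseline examination, and then identical settings will be used at follow-up", which makes the ratio sensible.

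**Conclusion.** The point holds as a gap in how the change is read: no interval, no stated link to repeat noise, and different scales for the two. It is worth correcting in the plan but does not undermine the design. At an assumed CV of 20% to 30% with averaged acquisitions, noise alone spreads the trial mean over roughly -7% to +11% and -9% to +19%. At CV 10% the range is only about -4% to +5%. These ranges assume lognormal, independent errors and all 20 patients with usable pairs.

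The upward shift from baseline noise is a secondary note. Its direction under independence is certain, but its size cannot be fixed from the documents. A reader might infer that the study is underpowered or that its estimate is wrong. Neither follows, because the plan claims no power and reports a median.

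**What to change.** In section 12.3, replace the sentence on large mean differences with:

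> For each perfusion measure, the two acquisitions at a visit are averaged; if only one is usable it is used, and the number of such visits is reported. The change from baseline to the 0-7 day scan is the lead contrast; baseline to 2-4 months is reported separately. The mean and the median of difference/baseline are each given with a 95% CI (t interval for the mean; order-statistic interval for the median, which for 20 pairs is the 6th to 15th values, 95.9%). These are exploratory estimates, read beside the spread of the repeat-acquisition relative changes. Repeats share one infusion and omit day-to-day variation, so this benchmark may be too small. A large mean without this comparison is not read as a SABR effect. If the mean and median disagree, the median is preferred, because noise in the baseline raises the mean.

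With fewer pairs, use the 5th to 14th values for 18 (96.9%) or the 5th to 13th for 17 (95.1%). The count of usable repeats is already close to a planned output: "Calculation of proportion of 3D DCE-US examination in which repeated scans is successful". A log-ratio summary may be added as a sensitivity analysis, labelled as a geometric mean change.

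Cost: a wording change and slightly more analysis, with no extra scans, visits or patients. All planned descriptive outputs stay. The drawback is that the median's interval is wider, about 28 against 23 points at CV 30% for a true 20% fall.

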12.4 Sample Size

20 patients.

12.5 Sample size justification

This study is an exploratory study and there is currently not sufficient information to perform a sample size calculation.

14 APPENDICES

14.1 APPENDIX A: Participant Eligibility Checklist

I. Protocol Information

Protocol Title:	Feasibility of 3D perfusion ultrasound of liver cancer SABR planning and response evaluation
Protocol Number:	IRB-30071 / HEP0048
Principal Investigator:	[name]

II. Subject Information:

Subject Name/ID:
Gender:  Male  Female

III. Inclusion/Exclusion Criteria

Inclusion Criteria	Yes	No	15 Supporting Documentation*
1. Ability to understand and willingness to sign the written informed consent document.			
2. Patient with primary liver tumor or metastasis scheduled for Stereotactic Ablative Radiotherapy (SABR)			
3. Patient is at least 18 years of age. No gender/race-ethnic restrictions.			
4. Performance status (ECOG) between 0-3			
5. History and Physical done within 4 weeks of enrollment.			
Exclusion Criteria			
1. Patient has previously been enrolled in and completed this study.			
2. Known right to left cardiac shunt, bidirectional or transient.			
3. Patient has any medical condition or other circumstances which would significantly decrease the chances of obtaining reliable data, achieving study objectives, or completing the study and/or post-dose follow-up examinations.			

4. History of hypersensitivity perflutren			
5. History of pulmonary hypertension			
6. Patients who are pregnant or are trying to become pregnant			

*All subject files must include supporting documentation to confirm subject eligibility. The method of confirmation can include, but is not limited to, laboratory test results, radiology test results, subject self-report, and medical record review.

IV. Statement of Eligibility

14.2 Appendix B

Definition of Menopausal Status:

Menopausal will be defined according to the following criteria:

Post-menopausal:

- Woman 60 years of age or older
- Woman aged 45-59 years with spontaneous cessation of menses for at least 12 months prior to registration
- Woman aged 45-59 years with cessation of menses for less than 12 months prior to registration AND an FSH level in the postmenopausal range (or >34.4 IU/L if institutional range is not available)
- Woman aged 45-59 years on hormone replacement therapy who have discontinued hormone replacement therapy at diagnosis of breast carcinoma and have an FSH level in the postmenopausal range according to institutional/laboratory standards (or 34.4 IU/L if the institutional range is not available)
- Prior bilateral oophorectomy
- Woman younger than 60 years of age who have had a prior hysterectomy (without bilateral oophorectomy) AND who have an FSH level in the postmenopausal range (or >34.4 IU/L if institutional range is not available)

Pre- or peri-menopausal: Not meeting definition for postmenopausal outlined above

14.3 Appendix C

ECOG Performance Status*

Grade	Description
0	Fully active, able to carry on all pre-disease performance without restriction
1	Restricted in physically strenuous activity but ambulatory and able to carry out work of a light or sedentary nature, e.g., light house work, office work
2	Ambulatory and capable of all selfcare but unable to carry out any work activities. Up and about more than 50% of waking hours
3	Capable of only limited selfcare, confined to bed or chair more than 50% of waking hours
4	Completely disabled. Cannot carry on any selfcare. Totally confined to bed or chair
5	Dead

* As published in Am. J. Clin. Oncol.:

